## 1. Introduction

End-stage renal disease (ESRD), or kidney failure, happens when the kidneys almost completely stop working, usually below 10-15% of normal function (1). It has been documented as a significant factor in rising rates of disability and mortality worldwide, particularly due to the rising rates of diabetes and hypertension(1).

Globally, the population of individuals with ESRD falls from 4.902 to 9.701 million, with most found in low and middle-income nations (1). In North Africa and the Middle East, ESRD rates exceed 500 per 100,000 population when age-standardized (2). In Gulf Cooperation Council (GCC) countries, the average rate of end-stage renal disease was 551 per million people, with Oman having the highest prevalence at 1000 per million and Qatar the lowest at 347 per million (3). In Kuwait, there were 465 cases of dialysis per million people, while the incidence of dialysis was 100 per million populations (4).

The Global Burden of Disease reports that impaired fasting plasma glucose, hypertension, sodium-rich diet, heart disease, urinary tract blockages, inflammation, and certain genetic disorders are common risk factors for end-stage kidney disease (1, 5). The last phase of chronic kidney disease necessitates renal replacement therapy, like dialysis or a kidney transplant, to ensure survival (1). Both forms of dialysis, hemodialysis or peritoneal dialysis, effectively eliminate toxins and excess fluids from the body, but they do not cure kidney disease (1). Nevertheless, hemodialysis is an extremely important treatment for individuals with ESRD that enhances health by removing toxins from the body, typically done multiple times a week and lasting several hours (1).

However, the lives of ESRD patients are impacted by hemodialysis treatment, which brings about various physical and psychosocial stressors during their lengthy

treatment (1). In relation to physical indications, hemodialysis patients are constantly in danger of experiencing intradialytic hypotension, muscle cramps, headache, fatigue, nausea, vomiting, itching, acute hemolysis, air embolism, bloodstream infections, and vascular access stenosis (6). While stress, insomnia, depression, and anxiety are among the psychological indicators in this group (7, 8). Additionally, most of these individuals have observed elevated amounts of pro-inflammatory markers in the blood, like C-reactive protein (9). In this situation, continual stress can harm the immune system by activating the hypothalamic-pituitary-adrenal (HPA) system, including hormones like cortisol, which rises 15 minutes after the stress situation and stays high for multiple hours (10, 11). During chronic stress and frequent exposure to stressors, a long-term elevation in cortisol levels can harm the hippocampus, reduce sensitivity to cortisol, and enhance cortisol binding to the mineralocorticoid receptor (12). When cortisol binds to the mineralocorticoid receptor, it triggers the release of pro-inflammatory factors like C-reactive protein (CRP) as a pro-inflammatory response (10) and psychological stress (13). It often leads to changes in body fluid balance, uremia, and frequent nocturnal muscle cramps, all of which disturb sleep (14). As the hemodialysis treatment often involves three or more sessions per week, each lasting several hours, it is taxing on the patient's body and disrupts natural circadian rhythms, compounding the effects of sleep disorders (14). Sleep disorders such as insomnia, restless leg syndrome, and obstructive sleep apnea are common among hemodialysis patients, leading to fatigue, cognitive decline, and increased risk for depression and anxiety (15). Additionally, poor sleep can exacerbate cardiovascular risks, worsen pain perception, and weaken the immune system, all of which are critical concerns for ESRD patients (16). These issues are particularly problematic because they affect patients' rest, physiological recovery, and mental

health (17). That's why sleep quality is often severely impaired in patients with ESRD, with rates of sleep disturbances much higher than in the general population or among those with other chronic illnesses (1).

As a result, reports have shown that ESRD patients sometimes employ ineffective or harmful coping strategies when facing multiple stressors, resulting in negative impacts on their overall physical and psychological well-being, increased vulnerability to infections, and higher rates of mortality and morbidity among this population (18, 19). On the other hand, mind-body techniques are believed to be beneficial for health by promoting a connection between the mind and body, enhancing present-moment awareness and acceptance without judgment (20).

Mindfulness meditation, a widely practiced mind-body technique, involves focusing on the present moment with an attitude of acceptance and nonjudgment (21).

Mindfulness meditation is hypothesized to target multiple cognitive and emotional processes that contribute to stress and poor sleep quality. It has been shown to enable psychological distance and positive reappraisals, helping to stop automatic, uncontrollable appraisals and decreasing stress and cortisol levels (22, 23). It has also been shown to decrease ruminative thoughts, diminish emotional reactivity, and promote impartial reappraisal of salient experiences, which together may facilitate sleep (24-27). In addition, it has been found to improve physiological indices of stress by cultivating stress and amygdala reactivity, resulting in decreased cortisol responses and pro-inflammatory markers such as CRP (28, 29). Decreased amygdala reactivity associated with activation of the parasympathetic nervous system decreases cortisol levels, which if high prolonged levels can cause an increase in glucocorticoid receptor resistance to cortisol and increased circulating markers of inflammation, such as CRP (30).

Smith (2005)(31) suggested in his Attentional Cognitive Behavioral (ABC2) Relaxation theory that two 30-minute sessions of mindfulness meditation per week are necessary to induce relaxation, reduce stress, and enhance overall health on the broader community (31). His mindfulness format has been suggested as a standardized format with five consecutive parts, each lasting 5 minutes, for a total session time of 30 minutes (31). Research has shown that this mindfulness meditation is as successful as the more extended method in decreasing stress levels (9, 32) . Also, mindfulness meditation has been shown to be a suitable therapy that improves various aspects of well-being in Arabic societies (33). In general, studies have shown that mindfulness meditation is a proven method to decrease stress and biomedical markers and improve sleep quality in both ESRD and other chronic patients, impacting them physically, emotionally, and mentally (9, 32, 34-44).

Since mindfulness meditation offers the potential to address psychological and physiological symptoms in different patient groups, it has not been widely utilized in hemodialysis patients compared to other chronic illnesses (45). Further, sleep issues are often under-recognized in clinical care, especially with ESRD patients receiving hemodialysis despite their high prevalence and impact on health outcomes (46, 47). Additionally, no studies have been conducted to investigate mindfulness meditation's impact on sleep quality and stress levels and inflammatory markers such as serum cortisol and C-reactive protein among hemodialysis patients. Thus, it is essential to have efficient nursing strategies for managing hemodialysis to ensure the best possible care for this group (45, 48-50). Therefore, the main goal of this research is to assess how effective mindfulness meditation is in improving sleep quality, reducing stress levels, and impacting serum cortisol and C-reactive protein levels in end-stage renal disease patients undergoing hemodialysis. Practically, the findings of this

research could advise the Kuwaiti Ministry of Health on incorporating mindfulness meditation in Kuwait hospitals. Theoretically, the current study could also broaden the nursing field's understanding and address the existing literature gap on how mindfulness meditation impacts sleep quality, stress perception, cortisol levels, and C-reactive protein in hemodialysis patients in Kuwait and culturally similar countries to enhance disease satisfaction.

## **2. Method**

### **2.1. Design**

This study used a repeated-measures, randomized, parallel control design and was conducted between September 2024 and February 2025 in the dialysis center at Jahra Hospital, Kuwait. The recruitment took approximately ten weeks, and the data collection and intervention took approximately nine weeks. Fifty-six ESRD patients undergoing hemodialysis were recruited using simple random sampling. Jahra Hospital is a governmental hospital with one of the biggest dialysis centers in Kuwait, with a female ward, male ward, and isolation ward. The center holds 70 dialysis machines/beds, with an average of 30 patients managed daily. The location was chosen because of its capacity to supply an adequate number of participants for the planned research. So, the researcher discovered that conducting an interventional study by enrolling patients from multiple Kuwait hospitals was costly and required a significant amount of time. Additionally, the researcher focusing on evaluating the efficacy of this treatment for ESRD patients receiving hemodialysis in Kuwait should prioritize addressing factors impacting internal validity over those impacting external validity or generalizability. Choosing a homogenous sample from a single setting is a method that can be used to enhance internal validity (51).

The inclusion criteria for participation in this study were being a patient with ESRD undergoing hemodialysis three times a week for a minimum of one year, being aged 18 years old or over, having a urea reduction rate greater than 65% or Kt/V greater than 1.2 in the past month, and possessing Arabic literacy skills. The exclusion criteria included being a patient with cognitive dysfunction or mental retardation, suffering from rheumatoid arthritis, using a hearing aid, regularly consuming psychopharmacological drugs to reduce stress and improve sleep, participating in other psychological therapies at the time, or had prior formal training in mindfulness methods or a current meditation practice. Criteria for exclusion were built based on the chronic condition of the participants' status, which would make participation in the mindfulness sessions and home practice of mindfulness meditation problematic or distressing. Having serious psychiatric conditions, receiving psychopharmacological drugs, participating in other psychological or mindfulness therapies, or having severe hearing impairment would potentially risk failure in the intervention or limit participation in the mindfulness sessions. Further, patients with rheumatoid arthritis may have an increased burden of both age-related and disease-related cognitive decline, and elevated C-reactive protein levels may indicate an inflammatory process in the body (52, 53). The trial is reported in accordance with the CONSORT guidelines.

The required sample size was calculated using G-power version 3.1. Given a mixed-design (within groups and between groups) repeated measures ANOVA, power of 0.95, moderate effect size of 0.25, and  $\alpha$  of 0.05, the required sample size was 44 subjects. A similar study reported an attrition rate of 60% (54). Considering an expected attrition rate of 60%, 24 subjects should be added. Thus, the final required sample size was 68 participants.

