#### **2.4. Procedure**

First, the permission from the instruments used in the study was obtained. Recruitment of participants was conducted by one of the study researchers who supervised the intervention delivery after obtaining approval from the hospital administrators to conduct the study. The list of all hemodialysis patients' names for both male and female floors, including their personal information (age, contact number, dialysis unit/room, hemodialysis shifts/days, hemodialysis access, hemodialysis starting date, and other chronic diseases) were gathered from the selected dialysis center. After that, all participants' files were checked for the last month Kt/V scores to conduct the inclusion criteria and select the study sample. The study purposes and protocol were explained to the patients in detail. Patients who agreed to participate in the study and met the eligibility criteria were asked to sign a consent form. Participants then completed the study variables' baseline measurements (T0) using the self-report questionnaires and measurements with a research assistant with a bachelor's nursing degree and 10 years of nephrology nursing experience. Another study researcher with a PhD degree, who was not involved in the recruitment process and data collection, randomized the participants to the experimental group ( $n = 34$ ) or the control group ( $n = 34$ ), using a simple 1:1 computer-generated sequence. The study variables were measured four weeks post the

start of the intervention (immediately after the twelve session, T1) and at the end of the final session (T2) for both groups. The measurements of the study variables at T0, T1 and T2 were conducted by the same research assistant who was not involved in any other parts of the study and blinded to randomization allocation. All measurements were privately taken at the dialysis center.

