## **2.5. Data analysis**

SPSS version 25 (SPSS Inc., Chicago, Illinois, USA) was used to analyze the collected data. Prior to the main analysis, outliers and missing data were examined and managed as appropriate. Then, the assumptions of the statistical tests used, normality using a histogram graph, homogeneity of variance, and sphericity were checked and managed as appropriate. Mauchly's test of sphericity is used to assess whether the assumption of sphericity has been violated. When Mauchly's test of sphericity was significant ( $P < 0.05$ ), the degrees of freedom were corrected using Greenhouse-Geisser or Huynh-Feldt estimates of sphericity. The comparability of the two groups was evaluated in terms of demographic characteristics and the baseline measurements of the dependent variables using a *t*-test and Chi-square based on the measurements of the dependent variables. The main analysis was conducted with repeated-measures ANOVA (mixed design: within and between groups). A *P*-value of 0.05 was set as the significance level for the main analysis tests.

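### The 0.95 power is stated for a moderate effect, but on the scale that yields 44 subjects f = 0.25 is an arm difference of about 1.06 to 1.22 SD

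*Protocol*

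**What the plan says.** Protocol section 2.1 (Design) reports a G*Power 3.1 calculation: "Given a mixed-design (within groups and between groups) repeated measures ANOVA", with "power of 0.95, moderate effect size of 0.25", alpha 0.05, and the conclusion that "the required sample size was 44 subjects". The figure is then raised to 68 for attrition; the same section reports 56 patients recruited.

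Section 2.4 (Procedure) gives three measurements (T0 before randomisation, T1, T2) and allocation "using a simple 1:1 computer-generated sequence". Section 2.5 (Data analysis) adds: "The main analysis was conducted with repeated-measures ANOVA (mixed design: within and between groups)".

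The protocol does not say which effect in that model f = 0.25 refers to (group, time or group-by-time), what correlation between visits was assumed, or what difference in sleep quality, stress, cortisol or CRP the 0.25 stands for.

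**The concern.** Cohen's f of 0.25 is conventionally called medium, and for two arms compared once it equals a 0.5 SD difference. A reader will take the sentence to mean that the trial has 0.95 power for a difference of about that size. A comparison of two arms of 22 does not normally deliver that.

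In a mixed repeated-measures design the G*Power default multiplies f² by the number of visits divided by one minus the correlation. The same 0.25 then describes a much larger separation between arms.

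What is at stake is the reading of a null result. With 0.95 power claimed for a moderate effect, non-significance on any of the four outcomes would look like strong evidence that mindfulness has no moderate benefit.

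**Working it through.** **Inputs from the protocol.** f = 0.25, power 0.95, alpha 0.05, N = 44 (2.1); k = 2 arms at 1:1 and m = 3 visits, with T0 before randomisation, so the expected arm difference at T0 is zero (2.4). **Assumptions:** correlation ρ equal between all visits, sphericity, and a common SD at each visit.

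**1. Reproducing 44.** For the group-by-time interaction under the G*Power default:

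- λ = f²·N·m/(1−ρ), df1 = (k−1)(m−1) = 2, df2 = (N−k)(m−1).
- At ρ = 0.5 the multiplier m/(1−ρ) is 6, so at N = 44, λ = 0.0625 × 44 × 6 = 16.5 with df 2 and 84. Power is 0.956; at N = 42 it is 0.946. So N = 44.
- Other correlations with m = 3 give other sizes: 60 at 0.3, 36 at 0.6, 28 at 0.7. This is why 0.5 is inferred.

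Other routes give:

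| Option, f = 0.25 | N for 0.95 power |
|---|---|
| Time effect only, m = 3, ρ = 0.5 | 44 (compares no arms) |
| Interaction, m = 2, ρ = 0.6 | 44 |
| Between-groups test, m = 3, ρ = 0.5 | 142 |
| Interaction, f on the SPSS scale, m = 3 | 128 |

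**2. What f = 0.25 means as an arm difference.** With d_t the arm difference at visit t in SD units, f² is the mean over visits of ((d_t − mean d)/2)². The correlation does not enter.

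- Full effect at T1 and T2, pattern (0, D, D): f² = D²/18, so D = 0.25 × √18 = 1.06 SD. The pattern (0, 0, D) gives the same.
- Rising effect, pattern (0, D/2, D): f² = D²/24, so D = 0.25 × √24 = 1.22 SD.
- Even on the two-visit route to 44, pattern (0, D): f² = D²/16, so D = 1.00 SD.

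On the partial eta squared scale, λ = 16.5 corresponds to 16.5/(16.5 + 88) = 0.158, with 88 = 44 × 2. An f of 0.25 read directly on that scale is 0.0625/1.0625 = 0.059.

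**3. Interaction power for a 0.5 SD difference.** f² = 0.25/24 (rising) or 0.25/18 (full), so f = 0.102 or 0.118. At N = 44 and ρ = 0.5, λ = 2.75 or 3.67.

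| Analysed | ρ = 0.5 | Range over ρ |
|---|---|---|
| 44 | 0.29–0.37 | 0.22–0.28 (ρ 0.3); 0.35–0.45 (0.6); 0.45–0.58 (0.7); 0.63–0.76 (0.8) |
| 56 | 0.36–0.46 | not tabulated |
| 68 | 0.43–0.55 | 0.83–0.93 (ρ 0.8) |

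Simulation with 20,000 trials per scenario at N = 44 and ρ = 0.5 gave 0.28 for the rising pattern and 0.36 to 0.38 for the other two. Power of 0.95 at ρ = 0.5 would need about 188 (full effect) to 250 (rising) in total.

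**4. Moderate taken as f = 0.25 on other scales.** On the SPSS scale, λ = f²(N−2)(m−1): power is 0.51 at 44, 0.63 at 56 and 0.72 at 68. For the between-groups test at ρ = 0.5, power is 0.51 at 44 and 0.70 at 68.

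**The case against.** The strongest reply is that nothing has been miscalculated. The 44 follows from the stated inputs and the software defaults, 0.25 is the conventional medium f, and the protocol never names 0.5 SD as its target. All of that stands. This is a mismatch of effect-size scale, and a reader who infers an arithmetic error in the 44 would be wrong. What does not stand is the pairing of the label with 0.95 power: that power belongs to a difference of more than one SD, and the protocol gives no figure in outcome units from which a reader could tell.

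The second reply is that the correlation is unknown and the interaction reading is not the only route to 44. This also stands. The time-only test gives 44 as well, but would then power no comparison of arms. The 0.5 SD power figures move a good deal with the correlation, which is why a range is shown; the 1.06–1.22 SD figure does not move.

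A stronger reading would be that the trial misses a moderate effect more often than not. The documents do not support that in general. On the SPSS scale power is above one half at all three sizes; for 0.5 SD it reaches 0.55 at 68 with the full effect from T1, and exceeds one half at 44 if the correlation is 0.8.

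Finally, the protocol nowhere interprets a null result or says that partial eta squared will be reported. The harm is one of interpretation, not an error already made.

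**Conclusion.** The concern holds as a misdescribed power statement. Under the group-by-time reading that reproduces 44 with the three planned visits, the plan has 0.95 power for arms about 1.06 to 1.22 SD apart, not for a moderate difference. This rests on equal arms at T0 and same-direction effects at T1 and T2, and does not depend on the correlation.

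For effects conventionally called moderate, no arm comparison computed here reaches 0.95 at 44, 56 or 68 analysed. For 0.5 SD the range is 0.29 to 0.55 at correlation 0.5, and the highest value found is 0.93, at correlation 0.8 with all 68 analysed. Correlations above 0.8 were not examined. The correlation of 0.5 is an inference from the 44, not a protocol figure.

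A reader might also infer that the trial must be enlarged to 188–250. That does not follow: the protocol states no 0.5 SD target, and those sizes show only how far the stated power is from one.

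**What to change.** In the sample-size paragraph of section 2.1:

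- Name the effect tested (the group-by-time interaction, if that is what was used) and have the sponsor state the correlation and sphericity values entered. The 0.5 inferred here should not be written in unless confirmed.
- Replace the moderate label with the arm difference it represents, for example: 44 analysed participants give 0.95 power for a group-by-time interaction equivalent to a difference of about 1.1 to 1.2 SD between arms at follow-up, assuming a correlation of [sponsor's value].
- State the power for a 0.5 SD difference at the number actually analysed, over a range of correlations such as 0.3 to 0.8.

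The report should then not present a non-significant result as 95%-power evidence against a moderate effect.

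Enrolment, design and analysis stay as they are. The cost is a few sentences and a stated power that looks less favourable.

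### Adding 24 participants does not cover the stated 60% attrition (44 completers would need 110; 68 leaves about 27), and 56 recruited contradicts 34 + 34 = 68 randomised

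*Protocol*

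**What the plan says.** Section 2.1 (Design) gives the sample-size inputs as "Given a mixed-design (within groups and between groups) repeated measures ANOVA, power of 0.95, moderate effect size of 0.25", with alpha 0.05, and arrives at 44 participants. It then turns to dropout: "A similar study reported an attrition rate of 60% (54"). From this it concludes: "Considering an expected attrition rate of 60%, 24 subjects should be added. Thus, the final required sample size was 68 participants".

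Two other statements give participant numbers. Section 2.1 says: "Fifty-six ESRD patients undergoing hemodialysis were recruited using simple random sampling". Section 2.4 (Procedure) says that another researcher "randomized the participants to the experimental group ( $n = 34$ ) or the control group ( $n = 34"), after consent and baseline measurement. Both are in the past tense, and section 2.1 says the study "was conducted between September 2024 and February 2025", so they read as reports of what was done, not as targets.

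On missing data, section 2.5 says only: "Prior to the main analysis, outliers and missing data were examined and managed as appropriate".

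**The concern.** There are two separate problems.

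1. **The attrition allowance.** An allowance for dropout should leave the required number once the expected losses have occurred. With 60% expected to leave, fewer than half of 68 remain, and that is below 44. The stated power of 0.95 is then not what the plan delivers under its own assumption.

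2. **The counts.** More people cannot be randomised than were recruited, yet the document has 68 randomised out of 56 recruited. The number randomised is the denominator for attrition and for every result. A reader cannot tell whether the trial fell short of its stated 68 or reached it and kept 56 to the end.

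The required number in section 2.1 is a planning quantity and need not equal either count. The contradiction lies between the recruited and the randomised numbers.

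**Working it through.** **Inputs from the protocol.** Mixed-design repeated-measures ANOVA, power 0.95, f = 0.25, alpha 0.05, required N = 44, attrition 60%, 24 added, total 68 (section 2.1). Two groups and three measurements, T0, T1 and T2 (section 2.4). Recruited 56 (section 2.1); randomised 34 + 34 (section 2.4).

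**Inputs assumed.** The correlation between repeated measures (ρ) and the sphericity correction (ε) are not stated. I take ρ = 0.5 and ε = 1, then vary both.

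**Step 1: reproduce the 44.** For the group-by-time interaction with k = 2 groups and m = 3 times, the F statistic has df1 = (k − 1)(m − 1)ε, df2 = (N − k)(m − 1)ε and noncentrality λ = N·m·f²·ε/(1 − ρ).

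At N = 44: λ = 44 × 3 × 0.0625/0.5 = 16.5, df = 2 and 84, power 0.956. At N = 42 power is 0.946. So 44 is the smallest even N that reaches 0.95. The base figure is sound under these inputs.

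**Step 2: the attrition step.** This needs no assumption about correlation.

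- Needed to keep 44 at 60% loss: 44/(1 − 0.60) = 110, that is 66 added.
- Common mistaken rule, adding 60% of 44: 44 × 0.60 = 26.4, so 27 added, total 71. This does not give 24 either.
- Loss that an extra 24 covers: 24/68 = 35.3%.
- Left from 68 at 60% loss: 68 × 0.40 = 27.2.
- Left from 56 at 60% loss: 56 × 0.40 = 22.4.

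**Step 3: the counts.** 34 + 34 = 68, which is 12 more than 56. If 56 were the completers, attrition would be 12/68 = 17.6%.

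**Step 4: power at the numbers analysed** (ρ = 0.5, ε = 1).

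| Situation | N analysed | λ | Power |
|---|---|---|---|
| Plan's target | 44 | 16.5 | 0.956 |
| 68 randomised, 60% lost | 27 | 10.125 | 0.795 |
| 56 enrolled, 60% lost | 22 | 8.25 | 0.697 |
| 56 are the completers | 56 | 21.0 | 0.987 |

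**Step 5: sensitivity.** At N = 27, power is 0.643 with ρ = 0.3 and 0.955 with ρ = 0.7 (ε = 1). Those correlations would have required 60 and 28 participants, so they are not the settings behind 44. I searched ε from 0.5 to 1.0 (step 0.05) and ρ from 0.3 to 0.9 (step 0.002), keeping only settings where 44 is the smallest even N reaching 0.95. Power is then 0.784 to 0.810 at 27, 0.684 to 0.718 at 22, and 0.983 to 0.988 at 56.

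**The case against.** The strongest reply is that 44, 60% and 68 are jointly inconsistent, and the error may lie in the rate. The correct inflation formula at 35% gives 44/0.65 = 67.7, rounded up to 68, so 68 may have been computed properly from a rate that was then misreported. This is possible. But 60% appears twice, once tied to a cited study, and 35% appears nowhere. Writing in 35% because it fits would be back-solving. If the authors' records show that another rate was used, they can say so and document it.

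Second, the loss of power is conditional. The trial has been conducted, and what it can detect depends on how many completed T2, which the protocol does not report. The values 0.80 and 0.70 hold only if 60% left and only completers were analysed. That stands and limits the claim. It also limits what follows from 56 as enrolment: 56 exceeds 44 and tolerates 12/56 = 21% loss. At ρ = 0.5, power from 56 enrolled would be 0.963 at 18% loss, 0.946 at 25% and about 0.91 at 35%. Missing the stated 68 would therefore not by itself make the trial underpowered.

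Third, the power values rest on a reconstructed correlation and sphericity. This also stands, so the corrected text should use the authors' own inputs. The figures 110 and 27 do not depend on them.

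A separate analysis plan could settle how missing data are handled. It could not make 24 a sufficient allowance for 60% attrition, or reconcile 56 recruited with 68 randomised.

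**Conclusion.** Both errors hold as written and must be corrected.

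The attrition arithmetic is wrong by a wide margin: 68 against the 110 that the protocol's own assumptions require, leaving about 27 participants instead of 44. With completers only, and with any correlation and sphericity setting on the grid that reproduces 44, power falls from 0.95 to about 0.80 (0.78 to 0.81). The chance of missing an effect of f = 0.25 is then about 20% instead of 5%.

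The recruited and randomised counts differ by 12 in the impossible direction, and nothing in the document resolves this. Of the two errors this matters more for a trial already conducted, because it leaves the number of patients entered unknown.

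**What to change.** Correct the text; no further enrolment is called for.

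- **Section 2.1, sample size.** Keep 60% as the stated planning assumption. Say that 68 randomised at 60% attrition leaves about 27 completers, that power for f = 0.25 is then about 0.80 and not 0.95, and that 110 would have been needed to keep 44. State the correlation and sphericity used in the original G*Power run, and take the final power value from those inputs. Do not substitute a rate of 35% chosen to fit 68.
- **Sections 2.1 and 2.4, counts.** Report separately how many patients were recruited, how many were randomised to each group and how many completed T2. Correct whichever of 56 or 34 + 34 is wrong from the trial records. Keep the required number apart from these counts.

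The cost is a few sentences and a look at the enrolment and randomisation records. Design and conduct are unchanged. The price is that the stated planned power becomes less favourable.
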